5.4. Prior and Concomitant Therapy

Except as noted in the exclusion criteria, all medications (prescription or over-the-counter) that have been started prior to screening may be continued during the course of the trial. All medications, including investigational medications that are continued from the start of the trial, or that are started during the trial (other than the study medication), must be documented on the Concomitant Medication Page of the electronic Case Report Form (eCRF).

5.5. Removal of Subjects from Trial

Subjects must be removed from the trial if:

1. Informed consent is withdrawn; or
2. The investigator or the sponsor believes it is in the best interest of the subject to be removed from the trial.

Subjects may be withdrawn from the trial if a SAE occurs. The date and reason for discontinuation should be noted on the eCRF. Subjects who discontinue prematurely should be seen for a final evaluation.

5.6. Premature Termination of Trial/Closure of Center

The sponsor may discontinue the trial at any time. Reasons for discontinuation of the trial may include, but are not limited to, new information on safety or efficacy, requests from regulatory authorities, or changes in business priorities. Additional reasons for center closure may include, but are not limited to, excessive protocol violations, inadequate regard for subject safety, failure to follow recommended procedures (e.g., documentation), failure or inability to accommodate Avid/Contract Research Organization (CRO) monitors or to provide required access to data and source documents, staff turnover, inadequate staffing, and inadequate enrollment. Except in cases affecting subject safety, the investigator may complete final study evaluations for ongoing subjects. In all cases of center,

or study termination, appropriate steps will be taken to ensure the safety of study subjects.

6. PRODUCT RISK ASSESSMENT

The most up-to-date and complete information regarding the use of ¹⁸F-AV-1451 Injection can be found in the investigator's brochure.

In brief, ¹⁸F-AV-1451 Injection is an experimental imaging agent that will be used at relatively low (tracer) doses. However, because ¹⁸F-AV-1451 Injection is in the early stages of clinical investigation, it is recommended that subjects receiving ¹⁸F-AV-1451 Injection be followed closely by means of adverse event reporting and vital signs.

There are no data on the effects of ¹⁸F-AV-1451 Injection in human perinatal development. For this reason, females must avoid becoming pregnant. Females must use adequate contraceptive methods for 24 hours after administration of ¹⁸F-AV-1451 Injection. ¹⁸F-AV-1451 Injection must not be administered to females who are pregnant, or lactating. Males with female partners who are pregnant or of childbearing potential must agree to refrain from sexual activity for 24 hours following administration of ¹⁸F-AV-1451 Injection. Additionally, males must agree not to donate sperm for 24 hours following administration of ¹⁸F-AV-1451 Injection.

7. PROCEDURES AND METHODS

7.1. Assessment Periods (See Section 11.2, Trial Flow Chart)

The study will consist of the following sequence of activities:

7.1.1. Screening Visit: Visit 1

Screening may take place over several days. All screening assessments will preferably be performed within 60 days prior to the ¹⁸F-AV-1451 PET imaging session.

Screening assessments will include:

- Informed consent;
- Demographics (age, gender, education, race, ethnicity);
- Medical history, concomitant medications;

- Disease history (date/months since symptom onset, date/months since diagnosis, family history of relevant neurologic disease);
- An ECG will be performed to assess the subject’s cardiac status. If an ECG was performed within the last 12 months and is available for review, the ECG does not need to be repeated;
- Cognitive status interview, including MMSE;
- MRI of the brain, only for those subjects who do not have a prior MRI (obtained within one year of enrollment) available for submission to Avid and are able to tolerate one;
- Serum pregnancy test (women of childbearing potential);
- A physician will see the patient during the screening visit.
- Florbetapir F 18 PET scan (see section [7.1.1.1](#) for details)

7.1.1.1. Screening Florbetapir F 18 PET scan

The screening florbetapir F 18 PET scan is to be performed to assess for evidence of amyloid pathology and should be interpreted by the local reader prior to enrollment. Amyloid scans that have been obtained within 3 years of screening can be submitted for review by the local reader for enrollment criteria. If deemed interpretable, the subject would not need to complete the screening florbetapir F 18 PET scan.

- For women of childbearing potential, a negative pregnancy test must be obtained within 24 hours prior to injection; If screening serum pregnancy test obtained within 24 hours prior to injection, the pregnancy test need not be repeated.
- Height and body weight will be measured prior to injection.
- A physician or licensed/credentialed medical professional (that is, a PET technologist, imaging center nurse, or a regional equivalent) designated by the site principal investigator must see the subject prior to administration of Florbetapir F 18 Injection to determine if they are still suitable to undergo the scan;
- Vital signs will be taken (pulse rate, respiratory rate, supine blood pressure) immediately prior to injection of florbetapir F 18;
- Subjects will receive a single IV bolus injection of approximately 370 MBq (10 mCi) +10% of florbetapir F 18 followed by a saline flush. A 20-minute continuous, dynamic PET brain scan will begin approximately 50 minutes following the dose administration;
- A physician or licensed/credentialed medical professional (that is, a PET technologist, imaging center nurse, or a regional equivalent) designated by

Protocol ¹⁸F-AV-1451-A19: “¹⁸F-AV-1451 PET Imaging in Subjects with Frontotemporal Dementia”

the site principal investigator will see the subject prior to discharge from the imaging center to evaluate the subject’s readiness for discharge;

- A follow-up phone call to the subject, or designated decision maker, will be conducted between 2 or 3 business days of the imaging day, but not before 48 hours post-injection, to confirm subject well-being and to collect information about any new adverse events. If both of these days are not business days, the follow-up phone call can occur the following business day.

7.1.2. **¹⁸F-AV-1451 PET Imaging Visit: Visit 2**

The ¹⁸F-AV-1451 PET scan should be performed at least 16 hours apart from the Florbetapir F 18 PET scan due to the half-life of fluorine 18. The following assessments will be performed for all subjects:

- Females of childbearing potential will have a urine or serum pregnancy test prior to injection (the result must be negative for the subject to be administered ¹⁸F-AV-1451);
- A physician or licensed/credentialed medical professional (that is, a PET technologist, imaging center nurse, or a regional equivalent) designated by the site principal investigator must see the subject prior to administration of ¹⁸F-AV-1451 to determine if they are still suitable to undergo the scan;
- Vital signs will be taken in a supine position immediately prior to administration of ¹⁸F-AV-1451 (within 30 minutes prior to injection) and at the completion of imaging at discharge.
- Body weight will be measured prior to injection.
- Subjects will receive a single IV bolus injection of approximately 370 MBq (10 mCi) ¹⁸F-AV-1451 followed by a saline flush. A 30 minute dynamic image will begin approximately 75 minutes following the dose administration;
- Subjects will be observed continuously for signs of adverse events, or serious adverse events;
- A physician or licensed/credentialed medical professional (that is, a PET technologist, imaging center nurse, or a regional equivalent) designated by the site principal investigator will see the subject prior to discharge from the imaging center to evaluate the subject’s readiness for discharge;
- A follow-up phone call to the subject, or designated decision maker, will be conducted within 2 or 3 business days of the imaging day, but not before 48 hours post-injection, to confirm subject well-being and to collect information about any new adverse events. If both of these days are not

business days, the follow-up phone call can occur the following business day.

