7. Are patients who have received a radiopharmaceutical for imaging or therapy within the past 24 hours prior to either imaging session for this study.
8. Have evidence of amyloid deposition as demonstrated by a positive florbetapir F 18 PET scan.
9. Are patients who, in the opinion of the investigator, are otherwise unsuitable for a study of this type.

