Pre-existing conditions (i.e., undesirable experiences, signs or symptoms that begin prior to the Screening Visit) will be recorded on the medical history eCRF pages. During the study, site personnel will record any change in the condition(s) and occurrence and nature of any AEs. Signs and symptoms that are believed to be due to the pre-existing condition(s) (started prior to dose of study medication) do not have to be recorded in the AEs section of the eCRF, unless there is an increasing in frequency and severity. Additionally, signs or symptoms or changes in pre-existing conditions that occur outside the trial defined adverse event reporting period (e.g., between each imaging visit will be recorded in medical history).

An adverse event is any untoward medical occurrence associated with the use of a drug in humans, whether or not considered drug related. For the purposes of this study, untoward medical occurrences will be considered associated with the use of ¹⁸F-AV-1451, and thus be reported as adverse events, if they occur within 48 hours after administration of ¹⁸F-AV-1451. Untoward medical occurrences will be considered associated with the use of Florbetapir F 18 injection, if they occur within 48 hours after Florbetapir F 18 injection administration. Adverse events associated with the use of ¹⁸F-AV-1451 or Florbetapir F 18 injection will be recorded as treatment emergent relative to the respective drug. Adverse experiences that occur after administration of either drug but outside the 48 hour reporting window will not be reported unless the investigator believes they are attributable to the drug.

Trial-emergent adverse events are undesirable experiences, signs or symptoms that begin, or worsen in intensity or frequency, after the informed consent, and

Protocol ¹⁸F-AV-1451-A19: “¹⁸F-AV-1451 PET Imaging in Subjects with Frontotemporal Dementia”

prior to administration of study drug at the imaging visit. In order to capture possible adverse effects of trial participation, trial-emergent AEs will also be reported during the baseline imaging period but not during the 48 hour windows following the administration of ¹⁸F-AV-1451 or Florbetapir. These will be recorded on the adverse event pages.

The end of study, for the purpose of adverse event reporting, is defined as 48 hours after the last study drug administration.

Serious Adverse Event (SAE)

A SAE is an AE that results in one of the following outcomes or constitutes one of the following events:

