- Death;
- Initial or prolonged inpatient hospitalization (other than that required by protocol; “social hospitalization” or any hospitalization for non-medical reasons does not constitute a SAE);
- A life-threatening experience (that is, immediate risk of dying);
- Persistent or significant disability/incapacity;
- Congenital anomaly/birth defect;
- Considered significant by the investigator for any other reason.

Important medical events that may not result in death, be life-threatening, or require hospitalization may be considered serious adverse drug events when, based upon appropriate medical judgment, they may jeopardize the patient and may require medical or surgical intervention to prevent one of the outcomes listed in this definition.

Unexpected Adverse Event

An unexpected adverse event is an adverse event not previously reported or an adverse event that occurs with specificity, severity or frequency that is not consistent with the current IB.

Relationship to Study Drug

Investigators will be instructed to report their assessment of the potential relatedness of each adverse event to protocol procedure or study drug. The assessment of the relationship of an adverse event to the administration of the study drug is a clinical decision based on all available information at the time of the completion of the eCRF.

Intensity/Severity of an Adverse Event

Protocol ¹⁸F-AV-1451-A19: “¹⁸F-AV-1451 PET Imaging in Subjects with Frontotemporal Dementia”

In addition to assessing the relationship of the administration of the study drug to adverse events, an assessment is required, in order to determine the intensity (severity) of the event.

The following classifications should be used:

Mild:

A mild adverse event is an adverse event, usually transient in nature and generally not interfering with normal activities.

Moderate:

A moderate adverse event is an adverse event that is sufficiently discomforting to interfere with normal activities.

Severe:

A severe adverse event is an adverse event that incapacitates the subject and prevents normal activities. Note that a severe event is not necessarily a serious event; nor must a serious event necessarily be severe.

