4 STUDY DESIGN

4.1 General Design

This is a multicenter Phase I study in subjects diagnosed with symptomatic clinical syndromes with expected FTD pathology.

Subjects followed in a referral center research cohort for FTD will be contacted to participate and must provide informed consent before starting ¹⁸F-AV-1451-A19 study procedures. Diagnosis will be determined by companion study with detailed characterization provided by enrolling physician.

Screening assessments will be conducted over several days and preferably will be performed within 60 days prior to the Flortaucipir F 18 PET imaging session. The screening assessments will include demographic information, a medical assessment for eligibility, vital signs, ECG, a brief cognitive assessment [e.g. Mini-Mental State Examination (MMSE)], and Florbetapir F 18 Positron PET imaging.

A physician will evaluate the subjects prior to administration of Florbetapir F 18 injection to determine if they are suitable to undergo the scan. Upon confirmation, the subjects will receive a single IV bolus injection of approximately 370 MBq (10 mCi) Florbetapir F 18 followed by a saline flush. A 20-minute continuous, dynamic PET brain scan will begin approximately 50 minutes following the dose administration. The screening Florbetapir F 18 PET scan is performed to assess for evidence of amyloid pathology and should be interpreted by the local reader prior to enrollment. Amyloid scans that have been obtained within 3 years of screening can be submitted for review by the local reader for enrollment criteria. If deemed interpretable, the subject would not need to complete the screening Florbetapir F 18 PET scan.

The Flortaucipir F 18 PET scan should be performed at least 16 hours apart from the Florbetapir F 18 PET scan due to the half-life of fluorine 18. Subjects who qualify for the study will come to the imaging center at a later date and will have a catheter(s) placed for IV administration of Flortaucipir F 18. Vital signs will be taken in a supine position prior to administration of Flortaucipir F 18 (within 30 minutes prior to injection) and at the completion of imaging prior to subject discharge. Upon confirmation by physician on suitability of subjects to undergo the scan, the subjects will receive a single IV bolus injection of approximately 370 MBq (10 mCi) Flortaucipir F 18 followed by a saline flush. A 30 minute dynamic image will begin approximately 75 minutes following the dose administration.

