6.6.2.1 Classifications of Adverse Events

Severity of Adverse Events:

The severity of an AE will be graded as “Mild”, “Moderate” or “Severe”. AEs events recorded with missing intensity will be summarized as Severe, following worst case principle.

Relationship to study drug/protocol procedure:

An AE will be considered as related to Flortaucipir F 18 if they occur within 48 hours after administration of Flortaucipir F 18, and will be considered as related to Florbetapir F 18 if they occur within 48 hours after administration of Florbetapir F 18.

In addition, the investigator will assess the relatedness of an AE to protocol procedure.

Any missing relationship of an AE to study drug or protocol procedure will be considered to be related for the analysis, following worst case principle.

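### SAP 6.6.2.1 sets relatedness to each tracer by a 48-hour clock where the protocol asks for the investigator's judgement, so the by-tracer relatedness tables carry no causality information

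*Protocol*

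**What the plan says.** Flortaucipir is the SAP's name for the protocol's 18F-AV-1451.

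**Relatedness in the SAP.** Section 6.6.2.1 states: "An AE will be considered as related to Flortaucipir F 18 if they occur within 48 hours after administration of Flortaucipir F 18". It gives the same rule for florbetapir. It then adds that "the investigator will assess the relatedness of an AE to protocol procedure". It gives the investigator no stated part in relatedness to either tracer. A last sentence counts a missing relationship, to study drug or to procedure, as related. SAP 6.6.2 defines a TEAE as an event that occurs or worsens within 48 hours after either tracer. SAP 8.10.2 tabulates TEAEs as related or not related, separately for florbetapir, flortaucipir and protocol procedure.

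**Relatedness in the protocol.** Section 7.7.2 gives the 48 hours a different job. It starts from a definition that sets causality aside: "An adverse event is any untoward medical occurrence associated with the use of a drug in humans, whether or not considered drug related". It then says that untoward occurrences "will be considered associated with the use of Florbetapir F 18 injection, if they occur within 48 hours after Florbetapir F 18 injection administration", with a matching sentence for flortaucipir, and records such events as treatment-emergent for that drug. Causality has its own paragraph, under which the assessment of the "relationship of an adverse event to the administration of the study drug is a clinical decision based on all available information". Section 7.7 has investigators report that assessment for each event by electronic data entry. Section 8.2.2 plans a presentation of adverse events by relationship to treatment. SAP 5.2 declares no change from the protocol's analyses.

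**Spacing of the two tracers.** Protocol 7.1.2 says the flortaucipir scan "should be performed at least 16 hours apart from the Florbetapir F 18 PET scan due to the half-life of fluorine 18", and SAP 4.1 repeats the minimum. Exclusion 7 in Protocol 5.3.2 bars patients who have "received a radiopharmaceutical for imaging or therapy within the past 24 hours prior to either imaging session for this study", with no exemption for the study's own florbetapir.

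**The concern.** The protocol keeps two questions apart: did the event fall in the observation window, and did the drug cause it? SAP 6.6.2.1 answers the second with the first. The same 48 hours also define a TEAE, so a by-tracer table of related and unrelated TEAEs reports only which window an event fell in.

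The only secondary objective is to expand the flortaucipir safety database, and these are its causality tables. A reader of the study report would take a count of TEAEs related to flortaucipir as a clinical judgement. Under the SAP as written it is a count of events with onset in the 48 hours after injection, including any that the investigator judged to have another cause.

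**Working it through.** **1. The two documents side by side**

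| Question | Protocol | SAP |
|---|---|---|
| What do the 48 hours decide? | Which events are reportable and treatment-emergent (7.7.2) | The same (6.6.2), and also which are related (6.6.2.1) |
| Who decides relatedness to a tracer? | The investigator, clinically (7.7, 7.7.2) | The clock (6.6.2.1) |
| Who decides relatedness to procedure? | The investigator (7.7, 7.7.2) | The investigator (6.6.2.1) |
| What is tabulated? | Events by relationship to treatment (8.2.2) | Related or not related, for each tracer and for procedure (8.10.2) |

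**2. What the SAP rules imply together.** For a new-onset event, let a be the hours from florbetapir injection to onset and b the hours from flortaucipir injection to onset.

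- TEAE (SAP 6.6.2): 0 ≤ a ≤ 48 or 0 ≤ b ≤ 48.
- Related to florbetapir (SAP 6.6.2.1): 0 ≤ a ≤ 48.
- Related to flortaucipir (SAP 6.6.2.1): 0 ≤ b ≤ 48.

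The union of the two related sets is the TEAE set, so 100% of new-onset TEAEs are related to at least one tracer, whatever the investigator recorded. Protocol 7.1.1.1 accepts an amyloid scan from the past 3 years. A subject who enters that way and receives only flortaucipir has no a. For that subject TEAE and related to flortaucipir are the same condition, and the not-related cell is empty by definition. In a subject given both tracers, a new-onset TEAE can be not related to flortaucipir only by falling in the florbetapir window alone.

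The result is limited to new-onset events. A pre-existing condition that worsens within 48 hours is a TEAE, but the relatedness sentence speaks only of events that occur in the window.

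**3. Events in both windows.** For injections g hours apart, overlap = max(0, 48 − g).

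- g = 16: 48 − 16 = 32 hours.
- g = 24: 48 − 24 = 24 hours.
- g = 48 or more: 0.

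The 16-hour minimum runs from scan to scan. The florbetapir scan starts about 50 minutes after its injection and the flortaucipir scan about 75 minutes after its own. Counted start to start, the injections are 16 h + 50 min − 75 min = 15 h 35 min apart, so the overlap is still about 32 hours. A new event in the overlap meets both SAP rules and enters both related counts, and no rule or flag marks it. These hours show that moving from 16 to 24 hours would not end the double counting. They do not measure how many subjects or events are affected, which the documents do not give.

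**4. The spacing rules.** A gap of at least 16 but less than 24 hours meets 7.1.2 and breaks exclusion 7 as worded; 24 hours or more meets both. This takes the session in exclusion 7 to start at injection. If it started at the scan, the study's own dose would exclude everyone. The decay table in Protocol 4.4 follows from 2^(−t/109.77), with t in minutes: 60 gives 0.685, 120 gives 0.469 and 240 gives 0.220, as printed. At 16 hours, 2^(−960/109.77) = 0.0023, or about 0.86 of 370 MBq. At 24 hours, 2^(−1440/109.77) = 0.00011, or about 0.04 MBq. The decay reason given for 16 hours is sound.

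**The case against.** The best defence is that little is lost. Protocol 7.7 and 7.7.3 require the investigator's drug assessment, and the SAP's rule for a missing relationship to study drug presupposes a field for it. SAP 7.1 lists all eCRF data and SAP 8.10.2 lists all adverse events, so with at most 25 subjects causality can be read case by case. The clock over-attributes, in keeping with the SAP's worst-case conventions, so it cannot hide a flortaucipir signal. No hypothesis test uses these tables.

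All of that stands as a limit on the consequence. It does not make the rule right. The SAP nowhere says that the field feeds the tables, and its explicit definition says otherwise, so a programmer would have to choose between them. Worst-case handling of a missing assessment is also different from overriding one that was recorded.

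A reader might infer three stronger points, which the documents do not support.

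- *The 16-hour and 24-hour rules cause the double attribution, or harm the images.* Any gap under 48 hours produces an overlap, and the residual activity at 16 hours is about 0.23%. Exclusion 7 may well be meant for tracers from outside the study. The mismatch is one of wording.
- *A 32-hour overlap means that most events are counted twice.* It is a span of hours in the tightest permitted schedule. Double counting needs an in-study florbetapir dose, injections less than 48 hours apart and a new event in the overlap. No document plans next-day scanning; Protocol 5.1 speaks only of a later date.
- *Event onset relative to flortaucipir will be lost, because the florbetapir follow-up call may come after the second injection.* Protocol 7.7 already asks for start and stop dates and times, Protocol 7.1.2 has a professional see the subject before injection, and the flow chart marks adverse events at both imaging visits.

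**Conclusion.** The point holds: the relatedness rule in SAP 6.6.2.1 is wrong as written, and the severity is minor. It departs from Protocol 7.7.2 and empties the by-tracer relatedness tables of clinical content, so the analysis by relationship to treatment in Protocol 8.2.2 is delivered in name only. SAP 5.2 does not declare the departure.

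Its size is 100% of new-onset TEAEs by construction, at any scan spacing. The further effect, one event counted against both tracers, is confined to subjects injected less than 48 hours apart, and that number may be zero. Overall TEAE counts, severity and seriousness summaries, listings, the procedure-relatedness table and the imaging results are unaffected.

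The conclusion assumes that the tables would be programmed from the definition in 6.6.2.1. If the programmer used the investigator's field instead, the tables would be right and the SAP text would still be wrong. The spacing mismatch is a separate matter of wording with no shown consequence.

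**What to change.** In SAP 6.6.2.1 and 8.10.2:

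- Define relatedness to each tracer as the investigator's recorded assessment, and tabulate that.
- Keep the 48-hour window only to define TEAEs.
- Keep the rule that a missing relationship counts as related.
- Flag, in the table or the listing, any event that falls in both windows.

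This needs no new data if the assessment required by Protocol 7.7 was collected. Check first whether the eCRF asks about each tracer separately, since the protocol speaks of study drug in general. If there is one field, tabulate that assessment under the tracer in whose window the event began and rely on the flag for events in both. The cost is a few sentences of SAP text and one derived flag.

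As a tidy-up, state in exclusion 7 that it does not apply to study florbetapir. It then agrees with the 16-hour minimum in Protocol 7.1.2 and SAP 4.1, and sites keep their present scheduling freedom.
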